Asymptomatic PCR+ at baseline: Given the 20% prevalence of asymptomatic coronavirus infection, we will need to screen 250 subjects to accrue the target enrollment of 200 to address the primary endpoint. If the PCR test returns positive while the health care worker is enrolled on the study, the participant will be notified and offered to be removed from the study or to continue with the study medication. Baseline PCR+ subjects who decide to withdraw from the study will be asked to go to occupational health and seek the care of their primary physician. Their study medication will remain blinded and the subject will be asked not to take any additional study medication. For baseline PCR+ subjects who decide to continue on study, they will be asked to keep the daily pill diary. If these subjects are asymptomatic after one week of study medication, they will be asked to return to undergo an on treatment nasopharyngeal swab. If the subject develops symptoms on study medication after 7 days of treatment, the subject will be unblinded. If the subject was assigned to placebo, they will have the option to crossover and get treatment with HCQ 600 mg qd for up to 7 days. Weekly phone calls per the sub-study 3 schedule will continue during this time. AEs will be reported as planned for the study. Baseline PCR+ subjects will be replaced in the prevention study related to the primary objective of sub-study 3 and will not count towards the target accrual or interim analysis. Baseline PCR negative subjects who screen positive at the one month or two-month mark will be considered COVID-19 positive as it relates to the primary endpoint.

Asymptomatic PCR+ at one month: These subjects will count towards the primary endpoint of sub-study 3 as an infection event. Accordingly, they will be unblinded and if on placebo they will be allowed to crossover to HCQ 600 mg qd for 2 weeks. If the subject is assigned to HCQ and turns PCR positive while asymptomatic, the subject will be stopped from study drug and referred to occupational health for standard of care management of health care worker infection. Weekly phone calls will continue. If the subject remains asymptomatic after one month, he/she will return for the one-month swab.

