Clinical Symptom monitoring: Appropriately delegated and credentialed study team members (as example: CRC) will screen for symptoms 1X per week and if present will document the likely treatment related AEs. Follow up with an appropriately delegated and credentialed physician investigator will be undertaken for assessment and grading of events. Participants will be asked if there have been changes in vision such as distortions of blurred vision. Patients who develop COVID-19 symptoms will be instructed to go to occupational health for nasopharyngeal swab. The rate of conversion to PCR positive in each arm at the 2-month mark will be used to assess the primary endpoint.

Electrocardiogram Recordings: An electrocardiogram (12 lead or 6 lead) will be recorded at baseline prior to the initiation of the study drug. Those participants with an ECG in the last 6 months and no QTc prolonging medications do not need a repeat baseline ECG. One month after starting the study drug a repeat ECG will be performed to confirm excessive QTc prolongation has not occurred. If the QTc has prolonged to >500ms dose reduction as described below will be attempted to achieve a QTc of <500ms. Due to the long half-life of HCQ, study medication can be started before the baseline ECG is read.

Pill diary: Electronic pill diary will be turned in by the participant at the end of the study.

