Supplement 2 [name] et al.

Sponsor: [name]	
Institution: University of Pennsylvania	
Protocol Identifier:	PATCH Trial NCT04329923
File Type:	Statistical Analysis Plan (SAP)

Title: Hydroxychloroquine for Pre-exposure SARS-CoV-2 Prophylaxis among Healthcare Workers: A Randomized Clinical Trial

A sub-study of the Prevention and Treatment of COVID-19 with Hydroxychloroquine (PATCH)

Description:

- The SAP aims at describing the analysis planned for protocol NCT04329923 and the information to be reported for the clinical study.
- The SAP will describe the analysis on safety, efficacy and related endpoints for the present study.

Introduction

This document is a statistical analysis plan (SAP) of NCT04329923 PATCH trial sub-study 3: a double blind randomized controlled clinical trial of hydroxychloroquine for pre-exposure prophylaxis to prevent transmission of SARS-CoV-2. The SAP summarizes the study design and objectives and aims at providing a detailed description of the statistical analyses planned for the protocol.

Study Design

This study is a multi-center (phase 2), randomized, double blind, placebo-controlled, group-sequential trial that aims at studying the efficacy and safety of hydroxychloroquine (HCQ) 600 mg daily compared to inert placebo tablets with matched size/shape as a pre-exposure prophylaxis treatment for at-risk hospital-based adult health care workers (HCWs).

In the study, the investigators plan to recruit 200 HCWs who work full-time in the hospital setting, who will be randomly assigned to the trial group or the control group with a proportion of 1:1. The experimental group will be treated with HCQ and the control group will be treated with placebo. The subjects who pass the screening and meet the eligibility criteria will join the study and will receive study medication to take at home for eight weeks. All subjects will be contacted weekly by study staff to ensure compliance with study procedures and to monitor for adverse effects. At baseline, 4 weeks and 8 weeks, all subjects will undergo nasopharyngeal swab (NP) testing for SARS-CoV-2

Protocol amendments and statistical plan			
Protocol version	Date of Institutional Review Board Approval	Changes to sub-study 3	Changes to Statistical Plan
1	April 2, 2020		
2	April 21, 2020	Baseline, one month ECG	QTc change a new secondary endpoint
3	May 6, 2020	Expansion of eligibility criteria to health care workers beyond Emergency department and infectious disease ward	None

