The hypothesis will be tested using a one-sided test, with a z-score corresponds to the log of the odds-ratio for remaining uninfected between the two groups. We will obtain the estimate of the odds ratio, and 95% CI, from logistic regression.

Randomization process

The study is a randomized, double-blind controlled trial. Randomization will be conducted via the Penn Investigational Drug Service, following a block randomization strategy. Fixed blocks of 8 will be assigned using well-established proprietary software for clinical trials (Sealed Envelope, London UK). Randomization will be kept confidential at the IDS until the pre-specified interim and final analyses. If any SAEs occur or if subjects become SARS-CoV-2 positive, those subjects can be unblinded by written request of the PIs to the IDS team.

General

Statistical analyses will be performed using Stata v16, SAS ® software v9.4 or later, or R. All statistical analyses will mirror those of the treatment groups of Hydroxychloroquine (HCQ) and Placebo.

Without any other specification, all statistical tests will be conducted with a two-sided 5% error. The primary hypothesis will also be tested with a 5% type-one error, but that error will be one sided, corresponding to the nature of the interim analyses. Small portions of the type 1 and type 2 error will be spent on interim

analyses, following Hwang-Shih-DeCani alpha and beta spending rules, leaving error rates at the final analysis slightly reduced.

Prior to analysis, data will be screened, cleaned, and examined for outliers using standard methods. Demographic and outcome variables will be summarized overall and by treatment. Continuous measurements will be described by means \pm standard deviations or medians with minimum and maximum or the interquartile range (IQR). Binary outcomes will be described by frequencies and proportions (percentages).

The results of randomization will be examined by comparing treatment arms for demographic and other relevant variables, to test for incidental bias. We will use two-sample statistics (t-tests or Wilcoxon tests) or contingency table methods (chi-square or Fisher's exact tests) as appropriate.

Primary Analysis

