Upon completion of the trial and the necessary data cleaning, the dataset will be locked for final analysis. This may occur at the final sample size of N=200, or earlier in the case of a decision to halt for futility. This final analysis will be conducted by study staff under supervision of the PIs with full involvement of two study statisticians. PIs and statisticians will review all results and p-values before analysis is determined complete and before manuscript submission.

Analysis Set	Definition	Outcomes
Randomized patients	Any patient randomized	Demographics
Evaluable for primary outcome	Randomized covid-19 negative at baseline and took at least one dose of study drug, and either completed all study procedures or	Primary outcome
Evaluable for Safety	Randomized and took one dose of study drug	Adverse events
Evaluable for drug-induced QTc prolongation	Randomized COVID-19 negative at baseline, took at least one dose of study medication and had a baseline and one month EKG	Change in QTc
Evaluable for antibody prevalence	Subjects who had blood drawn at specified timepoint	Antibody prevalence

Missing Data

Missing data values will not be imputed. Only observed values will be used for data analysis and presentation.

Subject Disposition

The summary statistics of the subjects will include the following information:

- The number and percentage of subjects who complete the trial and who drop out before trial completion according to the treatment groups.
- The number and percentage of subjects per analysis population according to the treatment groups.

Protocol Deviations

All protocol violations will be listed. The sponsor and/or its designee will review the protocol violations before the database is locked, and determine whether the involved subjects will be excluded from the per protocol set.

Demographic and Baseline Variables

The following demographic and baseline variables collected prior to the start of study medication will be summarized by treatment group.

Sex

Age

Profession (MD, nurse, respiratory technician, etc)

Location of work (ICU, ward, emergency department, etc)

Past medical history

Baseline testing will include NP swab testing for SARS-CoV-2, serologic testing for antibodies against SARS-CoV-2, and ECG testing (protocol amended DATE to include as a baseline test).

Adverse event reporting

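### The SAP commits to no baseline adjustment for change in QTc, and it limits this safety outcome to baseline PCR-negative participants without giving a reason

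*SAP*

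**What the plan says.** The SAP's amendment table records, for protocol version 2, "QTc change a new secondary endpoint". The table of analysis sets under Final analyses names the outcome as change in QTc and defines its set as "Randomized COVID-19 negative at baseline, took at least one dose of study medication and had a baseline and one month EKG". The row above it, for adverse events, is wider: "Randomized and took one dose of study drug".

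No test, model or covariate is given for QTc. Three general statements bear on it:

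- SAP, General: unless stated otherwise, "all statistical tests will be conducted with a two-sided 5% error". Outcome variables are to be summarised by treatment, continuous ones by mean and SD or by median and range or IQR.
- Final protocol, section 12.2: secondary outcomes receive at least group summaries with 95% CIs. Regression is something the team may add as exploratory work.
- SAP, Missing Data: nothing is imputed.

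On the baseline recording, protocol section 8.4.2 says: "Those participants with an ECG in the last 6 months and no QTc prolonging medications do not need a repeat baseline ECG". The footnotes to the Sub-study 3 schedule (Table 6) also allow ECGs to be deferred.

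**The concern.** Two separate gaps affect how well the trial can estimate the effect of the drug on QTc.

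First, every member of the set must have a baseline QTc, so the covariate is already in hand, but nothing commits the analysts to use it. The documented minimum is an unadjusted comparison of group means. If that is what is run, the interval for the arm difference is wider than it need be. If adjustment is decided later, that is a choice made after the data are seen.

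Second, a drug-safety outcome is restricted by baseline infection status. Protocol section 10.1 makes all participants evaluable for toxicity from their first dose and applies the PCR condition only to the primary outcome. The version 5 row of the SAP's amendment table likewise ties that condition to the primary endpoint. Section 8.4.2 allows dosing before the baseline PCR result is back and lets baseline-positive participants continue, so these people are exposed to study drug. The QTc set leaves them out without saying why.

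**Working it through.** **Inputs from the documents.** Target: "the investigators plan to recruit 200 HCWs", allocated "with a proportion of 1:1", so 100 per arm. Baseline positivity, from protocol section 8.4.2: "Given the 20% prevalence of asymptomatic coronavirus infection, we will need to screen 250 subjects to accrue the target enrollment of 200".

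**Inputs not in the documents.** The SD σ of QTc and the correlation ρ between baseline and one month. I assume equal variances at the two times and take ρ from 0.3 to 0.9.

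**The plan's own figure.** 200 / (1 − 0.20) = 250, which matches. At most 250 − 200 = 50 baseline-positive participants are therefore left out of the QTc set.

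**Baseline adjustment.** Per-person variance:

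- change score: 2σ²(1 − ρ)
- regression on arm and baseline: σ²(1 − ρ²)
- ratio: (1 − ρ²) / [2(1 − ρ)] = (1 + ρ)/2

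| ρ (assumed) | Variance ratio | SE ratio | 200 people act like |
|---|---|---|---|
| 0.3 | 0.65 | 0.806 | 308 |
| 0.5 | 0.75 | 0.866 | 267 |
| 0.7 | 0.85 | 0.922 | 235 |
| 0.9 | 0.95 | 0.975 | 211 |

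The last column is 200 divided by the variance ratio. σ cancels.

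**Dropping the PCR condition.** The SE ratio is √(200/N), where N counts participants with both ECGs:

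- N = 250 (all 50 added): √0.80 = 0.894, SE lower by 10.6%
- N = 220: √(200/220) = 0.953, SE lower by 4.7%
- N = 210: √(200/210) = 0.976, SE lower by 2.4%

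**Both changes together, at the ceiling of 250.** The SE ratio is √[0.80 × (1 + ρ)/2], which is √0.52 = 0.72 at ρ = 0.3 and √0.76 = 0.87 at ρ = 0.9.

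**Cost of the wider set.** Suppose the added 20% show a fraction w of the arm contrast seen in the rest. Relative to the PCR-negative set, the expected test statistic is (0.8 + 0.2w)/√0.8.

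- Break-even: 0.8 + 0.2w = 0.894, so w = 0.094/0.2 ≈ 0.47.
- At w = 0: 0.8/0.894 = 0.894, a loss of about 11%.

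**The case against.** The strongest reply is that the plan does not say the change will be unadjusted. A reader might infer that QTc is to be analysed as a raw change score, but the documents do not support that. The SAP names an outcome and no method. Its sentence on t-tests and Wilcoxon tests concerns baseline comparability of the arms. Section 12.2 permits regression. A regression of change on arm and baseline would fit the wording and gives the same treatment estimate as regressing the one-month value. This stands: the gap is a missing commitment, not a wrong method.

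A reader might also infer that admitting baseline-positive participants has no downside because randomisation balances infection. That does not hold either. Under section 8.4.2 these participants may withdraw and stop study drug. If symptoms develop after 7 days they are unblinded, and those on placebo may take HCQ, possibly before the one-month ECG. Section 10.3 treats symptomatic positives differently by arm once unblinded: off study on HCQ, allowed to stay for a time after crossover from placebo. If that rule reaches baseline positives, having a one-month ECG could depend on arm. Randomisation balances who is infected at the start, not who is still on assigned treatment and recorded a month later.

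Nor can all dosed participants be kept. Without two ECGs there is no change value, and nothing is imputed. The figure of 50 is a ceiling.

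Finally, a weak correlation is plausible with baseline ECGs up to 6 months old, but no document gives a value, and at ρ = 0.9 the variance gain is only 5%. No sample size or power figure rests on QTc, and neither document's list of secondary objectives includes it. This limits the importance of the point without removing it.

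**Conclusion.** The concern holds as two modest omissions. The SAP does not commit to adjusting change in QTc for a baseline value that its own set requires. Adjustment would cut the variance by 5% to 35% relative to unadjusted change, for an assumed ρ of 0.9 down to 0.3 and equal variances. In large samples the adjusted estimate is never less precise than the change score, so the direction is secure although the size cannot be fixed from the documents.

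The PCR-negative restriction is real, unexplained and narrower than both the SAP's safety set and the protocol's toxicity definition. Relaxing it lowers the SE by at most 10.6%, and by about 2% to 5% if 10 to 20 extra ECG pairs are obtained. It also changes the population studied, and it would weaken the comparison if the added group showed less than about 47% of the contrast in the others. That argues for a supporting analysis, not for replacing the present set. This is a worthwhile refinement of a secondary safety outcome and does not touch the primary result.

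**What to change.** Add a short paragraph to the SAP:

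1. Compare one-month QTc (or change in QTc) between randomised arms by linear regression on arm and baseline QTc, two-sided 5%, reporting the adjusted difference with a 95% CI. The cost is one degree of freedom and no new data.
2. Keep the baseline PCR-negative set and state why it is used. Add a supporting analysis of all dosed participants with both ECGs, by randomised arm, whatever their baseline PCR.
3. State for both sets how ECGs recorded after stopping study drug or after placebo-to-HCQ crossover are handled, and report by arm how many participants lack a one-month ECG.

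Items 2 and 3 need some extra programming and reporting. The risk in item 2 is dilution of the arm contrast, so the two sets should be shown side by side.

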2.4 Low dose versus high dose HCQ. In HCQ studies in cancer patients we conducted population pharmacokinetic studies and pharmacodynamic studies and determined that 800-1200 mg daily was required to effectively and consistently impair the lysosome in peripheral blood mononuclear cells. Our PK studies determined that it took roughly 2 weeks to achieve steady state in cancer patients. For these reasons there is rationale to propose a high dose (600 mg po bid) prolonged schedule treatment (2 weeks). In contrast an in vitro study recently published which included PK-PD modeling extrapolated from published PK studies indicated that HCQ was very active against COVID-19 but only 400 mg po bid X1 followed by 200 mg po bid for 5-10 days was enough for treatment. A recent non-randomized open label French trial (Gautret et al Int. J Antimicrobial Agents 2020) showed that 600 mg qd of HCQ cleared virus in 70 % of mildly ill hospitalized patients compared to 12.5% at 6 days of control patients. This generates a major question in how to use this agent in different populations that can best be answered in this three-part placebo controlled randomized trial.

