Anterior nares specimen: Participants will self-collect these samples on day 0 (start date for HCQ) before the HCQ is taken, Day 3, and day 7

The PATCH Trial

Foam swab provided: Puritan 6" Sterile Standard Foam Swab w/ Polystyrene Handle (SKU # 25-1506 1PF)

Collection instructions: Use a single foam swab for collecting specimens from both nares. Insert foam swab into 1 nostril straight back (not upwards). Once the swab is in place, rotate it in a circular motion 2 times and keep it in place for 15 seconds. Repeat this step for the second nostril using the same swab. Remove foam swab and insert the swab into the supplied tube.

Storage instructions: The collected swab should be placed into the bag marked "Nares swabs collected" and the date and time of the swab collection should be filled out Redcap. The "Collected" bag is then placed in the freezer in the same sealed container as the oral fluid.

Specimen stability for all specimen types for all tests is now as follows:

Room temperature: 5 days

Refrigerated (2 °C–8 °C): 5 days

Frozen (-20 °C): 7 days

Frozen (-70 °C): Acceptable

Specimen pickup: At the end of quarantine, or end of study procedures, the nares swabs will be collected. And shipped to Quest Diagnostics to assess viral titers. Cold packs or dry ice should be used during collection and cold packs should be used during shipping to Quest.

Pill diary: When the participant is released from quarantine the electronic pill diary must be submitted electronically.

Monitoring co-inhabitants: Appropriately delegated and credentialed study team members (as example: Clinical Research Coordinator) will ask the participant about the status of co-inhabitants daily to 14 days after the quarantine is completed to determine if the participant's co-inhabitants did or did not have symptoms or tested positive for COVID-19.

8.4.2 Sub-Study 3:

SARS-CoV-2 testing: Hospital workers will be tested for SARS-CoV-2 virus by RT-PCR every month. This will be a nasopharyngeal swab that will be processed by Quest diagnostics performed during enrollment at one month and two months. This screening NP swab will provide results in EPIC for clinical action within 72 hours. Eligibility criteria to start study medication does not require a negative PCR result to return.

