4	May 24, 2020	None	None
5	June 23, 2020	1. DSMB charter 2. Clarification that PCR+ positive patients at baseline are not evaluable for primary endpoint 3. secondary objective of # shifts missed is removed 4. clarification that subjects that discontinue study medication can still complete study procedures	1. Independent DSMB recommends early termination or continued accrual 2. Evaluable patients for primary outcome finalized

Study Objectives

PRIMARY OBJECTIVES

Rate of COVID-19 infection (cumulative incidence) during eight weeks of treatment or followup, as determined by NP swab testing performed by study staff at the 4-week and 8-week timepoints OR confirmed positive NP swab testing via a CLIA-approved clinical test performed before the 8-week timepoint.

SECONDARY OBJECTIVES

Rate of treatment related adverse events, as patient-reported outcomes obtained during weekly telephone calls to all subjects, following the Common terminology criteria for adverse events version 5.0 (CTCAE v 5.0).

CORRELATIVE OBJECTIVE

To bank serially collected samples to enable correlative science related this trial

Statistical Hypotheses

We hypothesize that there will be a statistically significant fewer new SARS-CoV-2 positive cases in the HCQ-treated cohort compared to the placebo-treated cohort during the 8 weeks of follow up.

Sample size and statistical treatment

The transmission of SARS-CoV2 from patient to hospital worker depends on many factors including specifics of standard care to prevent transmission, but especially on the number of patients seen at a given hospital or outpatient practice. Across China the reported hospital worker infection rate is 3.8%, but in Wuhan it is reported as 58% at the height of the epidemic. We will use a 10% cumulative incidence as the null hypothesis. In order for HCQ to be considered effective our alternative hypothesis will be a 1% transmission rate. With a 1:1 randomization for the HCQ to control arms we would require a total of 200 hospital worker subjects total. With the placebo group of 100 subjects and the HCQ arm of 100 subjects, a one-sided z-test ($\alpha=0.05$) comparing the rates in the two groups would have 84% power to detect a significant difference when the difference in the population rates is at least 9%. The design is akin to a randomized phase II design and not a randomized phase III design.

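### Antibody prevalence in anyone bled mixes pre-trial with on-trial infection, and the SAP makes no use of serology to check infections that clear between the scheduled swabs

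*SAP*

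**What the plan says.** **Antibody outcome.** In the SAP (Final analyses, Analysis Set table) the set for antibody prevalence is "Subjects who had blood drawn at specified timepoint". By contrast, the visible text for the primary set reads "Randomized covid-19 negative at baseline and took at least one dose of study drug", and the QTc set also requires baseline negativity. The SAP section on demographic and baseline variables states: "Baseline testing will include NP swab testing for SARS-CoV-2, serologic testing for antibodies against SARS-CoV-2, and ECG testing". Protocol Table 6 schedules research blood at baseline, one month and two months, and a footnote lets the draws be deferred. Antibody prevalence is not among the SAP's objectives. The SAP's General section says that outcomes are summarised overall and by arm, and sets two-sided 5% tests by default. Neither document defines seroconversion.

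**Primary outcome.** Under the SAP's primary objective, infection is counted "as determined by NP swab testing performed by study staff at the 4-week and 8-week timepoints" or through a "confirmed positive NP swab testing via a CLIA-approved clinical test performed before the 8-week timepoint". Protocol 8.4.2 adds weekly symptom screening, with symptomatic participants sent for a swab, and counts an asymptomatic positive at one month as an event.

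**Testing interval.** Protocol 8.4.2 says "Hospital workers will be tested for SARS-CoV-2 virus by RT-PCR every month", while Protocol 7.4 describes a two-weekly SARS-CoV-2 assay.

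**Clearance.** Protocol 2.4 cites a non-randomised open-label study in which HCQ "cleared virus in 70 % of mildly ill hospitalized patients compared to 12.5% at 6 days of control patients".

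**The concern.** There are two gaps, and the same data could address both.

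First, a participant infected before entry counts as antibody-positive at week 8 whichever arm they joined. Such infections add the same amount to both arms on average and shrink the relative difference, so the serology says little about infection on treatment.

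Second, the primary endpoint is meant to include asymptomatic infection. Someone with no symptoms and no clinical test is found only if still PCR-positive at a scheduled swab. A drug that shortened positivity without preventing infection would lower the observed rate, and PCR alone cannot separate that from prevention. Serology could help to tell them apart, but the plan has no analysis that does so.

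**Working it through.** **The plan's own figure.** The SAP gives 84% power for 10% v 1% with 100 per arm, one-sided 5%. A one-sided Fisher exact test gives 84.8%, so that figure is not in dispute. The plan gives none for antibody prevalence.

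**1. Dilution.** Inputs from the SAP: 10% v 1% new infection, 100 per arm, two-sided 5%. Assumed: a share s seropositive at entry. Prevalence at week 8 = s + (1 - s) x incidence. Power is by exact binomial enumeration of the pooled z-test.

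| s (assumed) | Placebo v HCQ prevalence | Ratio | Power, prevalence | Seronegative per arm | Power, seroconversion |
|---|---|---|---|---|---|
| 5% | 14.5% v 6.0% | 0.41 | 53% | 95 | 83% |
| 10% | 19.0% v 10.9% | 0.57 | 37% | 90 | 81% |
| 20% | 28.0% v 20.8% | 0.74 | 22% | 80 | 75% |

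Example at 20%: 0.20 + 0.80 x 0.10 = 28.0%; 0.20 + 0.80 x 0.01 = 20.8%. A normal approximation gives 51/36/22% and 78/76/71%, against 80% with nobody seropositive at entry. Protocol 8.4.2 plans for 20% asymptomatic infection at baseline and lets baseline PCR-positive participants continue. Equating that 20% with seropositivity is an assumption.

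**2. Missed infections.** Assume no prevention and 10% true infection in both arms. A share u of infections never prompts a test (20/40/60%, assumed), and all others are detected. An untested infection starts at a uniform time within a 28-day interval and stays positive for an exponential time with mean m days. The next swab finds it with probability

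D = (m/28) x (1 - exp(-28/m)).

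Observed rate = 10% x (1 - u + u x D). The rejection probability uses the final one-sided boundary of 1.6664; adding the interim boundaries gives the same figures to this rounding. With equal full detection it is 4.9%.

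*Moderate case.* Protocol 13.1 gives median viremia in mild cases as 14-20 or 14-28 days, and in Sub-Study 1 aims at a halved median time to quarantine release. Viremia is not nasopharyngeal PCR positivity, so using these figures is an assumption. For a control median of 20 days, m = 20/ln 2 = 28.9 and D = 0.64. Halved on HCQ, m = 14.4 and D = 0.44. At u = 60% the observed rates are 10% x (0.4 + 0.6 x 0.64) = 7.8% and 10% x (0.4 + 0.6 x 0.44) = 6.6%. Across control medians of 14-28 days, the false-positive rate is about 6% (u = 20%), 7% (u = 40%) and 8-9% (u = 60%).

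*Extreme case.* Turn the day-6 clearance in Protocol 2.4 into exponential rates. Control: m = -6/ln(0.875) = 45 days, D = 0.744. HCQ: m = -6/ln(0.30) = 5 days, D = 0.177.

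| u (assumed) | Observed placebo v HCQ | False-positive rate |
|---|---|---|
| 20% | 9.5% v 8.4% | 8% |
| 40% | 9.0% v 6.7% | 14% |
| 60% | 8.5% v 5.1% | 23% |

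**3. What serology recovers.** In the extreme case, let serology find a fixed share of the infections that PCR misses.

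| Assumed capture | False-positive rate at u = 20/40/60% |
|---|---|
| 90% in both arms | 5-6% |
| 60% in both arms | 6/7.5/9% |
| 90% placebo, 60% HCQ | 6.5/8.6/11% |

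**The case against.** The strongest reply is that the plan promises less than this point assumes. A reader might infer that the SAP tests efficacy on antibody prevalence. It does not: the outcome is outside the objectives and has no named test, so the power figures show what a contrast by arm could deliver, not a failed planned test. Baseline serology could also be read beside later prevalence. That stands, but a side-by-side reading is not an analysis of new infection.

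A reader might also infer that infection before entry biases the comparison. Under randomisation it does not, unless deferrable draws are missed differently by arm.

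On detection, a reader might infer that the primary result is biased towards HCQ, or that infection is sought only by four-weekly PCR. The documents support neither. Positive clinical tests count and symptomatic participants are swabbed, so the gap is confined to asymptomatic, untested infections and deferred swabs. Faster clearance rests on one non-randomised study in hospitalised, already infected patients. Stretching it to mean positivity of 45 v 5 days in asymptomatic workers is a ninefold contrast, paired here with no prevention at all.

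The Protocol 5.0 statement that antibody results alone will not drive decisions sits under unblinding and does not bar a sensitivity analysis.

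**Conclusion.** The point holds as an improvement to the SAP, not as a demonstrated error in the primary analysis. Antibody prevalence at an unnamed timepoint, with no baseline-seronegative condition, is a weak summary of on-trial infection: about 53/37/22% power against 83/81/75% for seroconversion, at an assumed 5/10/20% seropositive at entry.

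Differential detection is a possibility. If HCQ speeds clearance, the direction would favour HCQ. The size is uncertain: a false-positive rate of about 6-9% under a halved median positivity, and 8/14/23% only under the extreme extrapolation. Both depend on the assumed 20/40/60% of infections never prompting a test and on swabs at weeks 4 and 8. The two testing intervals in Protocol 7.4 and 8.4.2 must be reconciled.

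**What to change.** In the SAP's Analysis Set table, replace antibody prevalence with: *seroconversion by 8 weeks among participants antibody-negative at baseline, by randomised arm*. Name the blood draws used and define seroconversion.

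Prespecify, before unblinding, one supportive sensitivity analysis: *PCR-positive or seroconverted by 8 weeks, among participants PCR-negative and seronegative at baseline, by randomised arm*. Leave the primary analysis unchanged. Report missing blood draws by arm. Reconcile Protocol 7.4 with 8.4.2 on the testing interval.

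The cost is SAP wording and one more analysis of samples already scheduled. There are limits. Draws can be deferred and missing values are not imputed. Infections late in the 8 weeks may not yet have seroconverted. The check removes the detection problem only so far as serology captures infections equally in both arms.
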